# 10.2 Lost to follow up

For Phase 1a, lost to follow-up will not be defined considering the nature of the project; participants are working collaboratively with the research team to adapt the intervention and it is anticipated that there will be little to no loss of participants. For Phase 1b, where participants are asked to respond to an online survey or participate in an interview, there is no follow-up period, and therefore, this is also not defined.

For Phase 2, here is only a single follow-up period for this study which is within 4-weeks of the completion of the intervention. A participant will be recorded as lost to follow-up if they do not complete the post intervention follow-up data collection.

For those who do not adhere to the treatment protocol within Phase 2, we will collect data as per the protocol.

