# **14 Statistical considerations**

#### 14.3 Sample size

Phase 1a: We will establish an Intervention Adaptation Group (IAG) comprised of 6 to 8 key stakeholders who will be representatives from our PPI partners, carers and family members, people with LD, and clinicians, along with members of the research team. These participants will work with use to adapt and refine our intervention, measures, and fidelity checklist. There are no research data for formal analyses being collected from these participants.

Phase 1b: We will collect data about TAU from a minimum of 50 parents, together with LD health professionals, service providers, and commissioners).

Phase 2: We will recruit up to 20 participants and their parental caregivers in total. As this is a feasibility study, and the purpose is to provide estimates of key parameters for a future pilot trial rather than to power the current study to detect statistically significant differences, a formal a priori power calculation will not be conducted (54).

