### 14.7 Progression criteria

The study will estimate key parameters for a future trial that will be used to inform HTA decisionmaking with regard to advertising for a future trial and will assist researchers in developing proposals for a future trial. We propose the following progression criteria with reference to several key indicators of success: (a) recruitment, (b) protocol adherence, and (c) outcome data. These have been incorporated into three possible recommendations regarding feasibility of a larger trial (63).

Evelina London

**Green.** If all of the following criteria are met, the Study Steering Committee (SSC) will consider a recommendation that a larger trial is feasible:

(a) Recruitment: (i) accrual rate is at least 3 patients per site per month on average, and (ii) attrition rate is 30% or lower,

(b) Protocol adherence: (i) fidelity ratings indicate therapist adherence to the intervention of at least 75%, (ii) at least 70% of parents/carers and clinicians report that the intervention and consent procedures were acceptable, and (iii) at least 90% of participants received the intervention, and

(c) Outcome data: (i) at least 75% of participants complete outcome measures at each time point, (ii) at least 75% of items across outcome measures for each participant are complete, and (iii) at least 75% of parents/carers judge the outcome measures to be acceptable.

**Amber.** If any of the following criteria are met, then the research team will examine the reasons for this, carefully consider what remedial action can be taken to improve the likelihood that a larger trial is feasible, and provide this analysis to the SSC for consideration. For example, difficulties may be related to a delay in research ethics or governance approvals or a longer than expected time to build relationships with referrers which could be managed effectively within a larger trial:

(a) Recruitment: (i) accrual rate is less than 3 but greater than 2 patients per site per month on average, or in the later recruitment months the accrual rate reaches 3/month and (ii) attrition rate is greater than 30% but less than 50%,

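### Section 14.7: the attrition and outcome-completion bands do not line up, the Amber and Red attrition bands overlap, and completion of 50% to 60% falls in no band

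*Protocol*

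**What the plan says.** Section 14.7 sets traffic-light criteria for the recommendation on a larger trial. On attrition, item (a)(ii), Green is where "attrition rate is 30% or lower". Amber is where "attrition rate is greater than 30% but less than 50" per cent, and Red is anything above 40%. On completion of outcome measures, item (c)(i), Green is where "at least 75% of participants complete outcome measures at each time point". Amber is above 60% and below 75%, and Red is below 50%. Item (c)(ii) adds, for Green, that "at least 75% of items across outcome measures for each participant are complete".

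The combination rules differ by colour. For Green: "If all of the following criteria are met, the Study Steering Committee (SSC) will consider a recommendation that a larger trial is feasible". For Amber: "If any of the following criteria are met, then the research team will examine the reasons for this". Red also uses an any-criterion rule and may lead to a recommendation not to proceed.

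Section 14.7 does not define attrition and gives no denominator for (c)(i). The nearest definition is in section 10.2: "A participant will be recorded as lost to follow-up if they do not complete the post intervention follow-up data collection". There is only one follow-up. On size, section 14.3 says: "We will recruit up to 20 participants and their parental caregivers in total".

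**The concern.** Under the section 10.2 definition, a family lost to follow-up and a family without follow-up outcome data are the same family. One observed quantity is then judged twice, against limits that are not complements: 30% attrition corresponds to 70% completion, but Green completion starts at 75%. The Study Steering Committee would be shown a 30% tolerance that another line of the same list takes away. Further down, the attrition bands overlap and the completion bands leave a gap.

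The feasibility recommendation is a main product of Phase 2. Bands that overlap or leave a gap allow the colour of a result to be argued after the data have been seen.

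**Working it through.** The protocol has no calculation to reproduce here; its only figures are the thresholds.

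**Inputs.** N = 20, the maximum (14.3). Attrition bands: Green ≤30%, Amber >30% to <50%, Red >40% (14.7). Completion bands: Green ≥75%, Amber >60% to <75%, Red <50% (14.7). Loss means no completed follow-up collection (10.2). Two assumptions are needed: that attrition means this loss, and that both rates use all enrolled families.

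**Formulae.** With L families lost, attrition = L/20 and follow-up completion = (20 − L)/20 at most.

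| Lost | Attrition | Band (a)(ii) | Completion | Band (c)(i) |
|---|---|---|---|---|
| 5 | 25% | Green | 75% | Green |
| 6 | 30% | Green | 70% | Amber |
| 7 | 35% | Amber | 65% | Amber |
| 8 | 40% | Amber | 60% | none |
| 9 | 45% | Amber and Red | 55% | none |
| 10 | 50% | Red | 50% | none |
| 11 | 55% | Red | 45% | Red |

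**Green mismatch.** Only L = 6 is Green on attrition and not Green on completion. The largest loss that is Green on both is 5 of 20, or 25%. Over final sample sizes of 10 to 21, there is one such count at 10, 11, 14, 15 and 17 to 21, and none at 12, 13 or 16.

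**How often it would matter.** P(exactly 6 lost) = C(20,6) × q^6 × (1 − q)^14, where q is the true attrition. The protocol gives no expected q, so a range is assumed.

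| Assumed q | P(6 lost) | P(Green on (a)(ii)), L ≤ 6 | P(Green on (c)(i)), L ≤ 5 |
|---|---|---|---|
| 30% | 0.192 | 0.608 | 0.416 |
| 25% | 0.169 | 0.786 | 0.617 |
| 20% | 0.109 | 0.913 | 0.804 |
| 15% | 0.045 | 0.978 | 0.933 |

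**Overlap and gap.** These need no assumption about what attrition means. Amber attrition runs up to 50% and Red starts above 40%, so every value above 40% and below 50% lies in both; at n=20 that is 9 families. Amber completion stops above 60% and Red starts below 50%, so values from 50% to 60% inclusive lie in neither; at n=20 that is 10, 11 or 12 completers. The gap lies within (c)(i) itself and would exist whatever the attrition limit was.

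**The case against.** The strongest reply is that section 14.7 never says attrition is loss to follow-up. Section 10.1 allows a family to leave the intervention only, and section 12.2 provides for collecting outcome data from families who stop treatment. Section 5.2 lists attrition and response rates to the measures separately. If attrition counts withdrawals, 6 withdrawals of whom 4 still give data is 6/20 = 30% attrition with (20 − 2)/20 = 90% completion, and nothing conflicts. This stands. A reader might infer that the 30% limit is inoperative under every reading; the documents do not support that. It is inoperative only under the section 10.2 meaning with a common denominator.

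A second reply is that the all-criteria rule for Green settles the matter: 6 lost is Amber overall. This also stands. The Green mismatch is a limit overridden by a stricter one, not an undecidable result.

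A reader might also infer that (c)(ii) contradicts both other criteria, because a lost family with a full baseline has only half its items. That requires every enrolled family to be counted and equal item sets at two time points to be pooled. As a mean over families, 6 lost gives (40 − 6)/40 = 85%, which passes; among returned questionnaires, loss has no effect. The text does not choose between these readings, so (c)(ii) lacks a summary rule, which an analysis plan commonly supplies. It is not a contradiction.

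Finally, the study is descriptive and the colours guide a discussion. That limits the severity. It does not remove the overlap or the gap, which are numeric limits fixed in the protocol itself.

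**Conclusion.** The point holds in a limited form. The overlap on attrition (above 40% and below 50%) and the gap on completion (50% to 60% inclusive) are wrong as written under any definition. The Green mismatch of 30% against 75% depends on attrition meaning loss to follow-up over all enrolled families. On that basis it lowers the effective Green limit to 25%, at one count (6 of 20), with a probability of about 0.05 to 0.19 if true attrition is 15% to 30%. Calling 6 lost Amber overall, and 9 lost both Amber and Red, treats each numbered item as a criterion in its own right.

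No estimate and no safety decision changes. Severity is minor to moderate: the bands should be corrected before results are seen, but they do not undermine the study.

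**What to change.** In section 14.7, define attrition as loss to follow-up in the sense of section 10.2, divided by all enrolled families, and use the same denominator for (c)(i). Replace the two sets of bands with one contiguous scale built from limits already stated there:

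| | Attrition | Completion |
|---|---|---|
| Green | 25% or lower | at least 75% |
| Amber | above 25% to 40% | 60% to under 75% |
| Red | above 40% | under 60% |

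At n=20 this makes 0 to 5 lost Green, 6 to 8 Amber and 9 or more Red, on both measures. Families who leave treatment but still give data should be reported separately, so that they are not counted as attrition. As a minor clarification, state that (c)(ii) is summarised among returned questionnaires, so that non-return is not counted again.

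The change is to wording only, but it moves some boundaries and should say so. The Green attrition limit becomes slightly stricter (25% instead of 30%). Completion of 50% to under 60%, now in no band, becomes Red, and exactly 60% becomes Amber. Attrition above 40% and below 50%, now both Amber and Red, becomes Red only. Aligning Green at 30% and 70% would also remove the mismatch, at the price of loosening the completion requirement.

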(b) Protocol adherence: (i) fidelity ratings indicate therapist adherence to the intervention is less than 75% but greater than 60%, (ii) less than 70% but greater than 55% of parents/carers and clinicians report that the intervention and consent procedures were acceptable, and (iii) less than 90% but greater than 70% of participants received the intervention

(c) Outcome data: (i) less than 75% but greater than 60% of parents/carers complete outcome measures at each time point, (ii) less than 75% but greater than 60% of items across outcome

measures for each participant are complete, and (iii) less than 75% but greater than 65% of parents/carers judge the outcome measures to be acceptable.

**Red.** If any of the following criteria are met, and following a thorough review of the reasons for this, including consideration as to whether remedial action could be taken, a recommendation to not proceed to a larger trial may be made by the SSC:

Reading A University of East Anglia

(a) Recruitment: (i) accrual rate is less than 2 patients per site per month on average, and (ii) attrition rate is greater than 40%,

(b) Protocol adherence: (i) fidelity ratings indicate therapist adherence to the intervention is less than 50%, (ii) less than 55% of parents/carers and clinicians report that the intervention and consent procedures were acceptable, and (iii) less than 60% of participants received the intervention, and

(c) Outcome data: (i) less than 50% of parents/carers complete outcome measures at each time point, (ii) less than 50% of items across outcome measures for each participant are complete, and (iii) less than 65% of parents/carers judge the outcome measures to be acceptable.

All recommendations will be made to the Study Steering Committee, including our analysis of associated barriers and proposed remedial action

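### Progression bands in section 14.7 overlap for attrition, leave four ten-point gaps, and have no clear combination or precedence rule

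*Protocol*

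**What the plan says.** Protocol section 14.7 judges eight sub-criteria in three blocks: (a) recruitment, (b) protocol adherence and (c) outcome data.

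- **Green** is conjunctive: "If all of the following criteria are met, the Study Steering Committee (SSC) will consider a recommendation that a larger trial is feasible".
- **Red** opens with: "If any of the following criteria are met, and following a thorough review of the reasons for this". Amber also opens with *any*. In both bands, however, the sub-items within a block are joined by *and*.
- **Attrition:** Amber is "attrition rate is greater than 30% but less than 50" per cent; Red is "attrition rate is greater than 40" per cent.
- **Receipt of the intervention:** Amber is "less than 90% but greater than 70% of participants received the intervention"; Red is "less than 60% of participants received the intervention".
- **Outcome completion:** Amber is "less than 75% but greater than 60% of parents/carers complete outcome measures at each time point"; Red is "less than 50% of parents/carers complete outcome measures at each time point". Fidelity and item completeness use the same pair of limits, 60% and 50%.

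The section does not say which band prevails when a result meets both Amber and Red. It does say that all recommendations go to the Study Steering Committee (SSC), and that Red may, after review, lead to advice not to proceed.

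**The concern.** Progression criteria are useful because the mapping from result to band is fixed in advance. Here some attainable results map to two bands and others to none. The combination wording can also be read in two ways that give different answers. Someone would then have to decide the band with the results in hand. Section 14.7 is the protocol's only progression rule, and it is meant to inform the funder's decision on a larger trial.

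**Working it through.** **Inputs.** The limits come from section 14.7. Phase 2 recruits up to 20 participants (section 14.3) at 2 sites (Synopsis). Planned accrual is about 3 per month over seven months (section 9.3). There is no plan figure to reproduce, since the protocol makes no power calculation.

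**Step 1: set the limits side by side.**

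| Sub-criterion | Green | Amber | Red | Two bands | No band |
|---|---|---|---|---|---|
| Accrual per site per month | ≥3 | >2 and <3 | <2 | – | exactly 2 |
| Attrition | ≤30% | >30% and <50% | >40% | >40% and <50% | – |
| Fidelity | ≥75% | >60% and <75% | <50% | – | 50-60% |
| Intervention/consent acceptability | ≥70% | >55% and <70% | <55% | – | exactly 55% |
| Received intervention | ≥90% | >70% and <90% | <60% | – | 60-70% |
| Outcome completion | ≥75% | >60% and <75% | <50% | – | 50-60% |
| Item completeness | ≥75% | >60% and <75% | <50% | – | 50-60% |
| Measure acceptability | ≥75% | >65% and <75% | <65% | – | exactly 65% |

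The gaps include both ends. The accrual row leaves out Amber's alternative clause about later months reaching 3 per month. That clause drops the per-site unit and could hold while the average is below 2.

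**Step 2: convert to counts with 20 participants** (5 points per participant).

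- Attrition: 9/20 = 45% is Amber and Red. 8/20 = 40% is Amber only, and 10/20 = 50% is Red only.
- Received: 12/20, 13/20 and 14/20 = 60%, 65% and 70% have no band.
- Completion: 10/20, 11/20 and 12/20 = 50%, 55% and 60% have no band.

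**Step 3: apply the whole rule under both readings**, with every sub-criterion not named held at Green.

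| Result | *Any* single sub-criterion suffices | All sub-items in a block needed |
|---|---|---|
| Attrition 45% | Amber and Red | none |
| Attrition 60% | Red | none |
| Accrual 1 per site per month | Red | none |
| Received 65% | none | none |
| Fidelity 55% | none | none |
| Completion 55% | none | none |
| Item completeness 55% | none | none |
| Fidelity 70% with measure acceptability 60% | Amber and Red | none |

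The four interval gaps do not depend on the reading. The last row shows that, under *any*, one Amber and one Red sub-criterion trigger both verdicts. A precedence rule is therefore needed even once the bands are contiguous. One caveat applies to completion: a shortfall at follow-up would usually move attrition off Green too, because section 10.2 defines loss to follow-up as not completing that assessment.

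**Step 4: how likely are such results?** These are illustrations under assumed true rates; the protocol gives none.

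- Attrition 30%: P(9 of 20 lost) = C(20,9) × 0.3⁹ × 0.7¹¹ = 167,960 × 0.000019683 × 0.019773 ≈ 0.065.
- Receipt 85%, 80% or 75%: P(12 to 14 of 20 treated) ≈ 7%, 19% or 34%.

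**Step 5: accrual unit.** Section 14.7 counts per site; section 9.3 plans an overall rate. Recruitment exactly to plan is 20 / (2 sites × 7 months) = 20/14 ≈ 1.4 per site per month, below the Red limit of 2.

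**The case against.** The strongest defence is that the bands are advisory. Under Green the SSC considers a recommendation, and under Red one may follow after reasons and remedies are reviewed. A result in a gap is at least clearly not Green. This stands, and it limits the consequence: no automatic stop or go depends on the label. But the discretion concerns what to do once a band is known. It does not say which band applies.

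A second defence is that the lead-ins settle the logic and *and* is ordinary list grammar. That is a fair reading, and under it very slow accrual with low attrition is Red. A reader might infer that such a result is definitely neither Red nor Amber, but that holds only if *and* overrides *any*. The supportable claim is ambiguity.

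Third, a statistical analysis plan might tidy this up. It could resolve the attrition overlap only by departing from one of the protocol's stated limits.

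Three stronger inferences are also unsupported:

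- **That about 21% of studies with 30% true attrition would end in contradiction.** The chance of 8 to 10 lost is indeed 0.114 + 0.065 + 0.031 ≈ 0.21. With other criteria Green and under *any*, however, 8 lost is Amber and 10 lost is Red, even if completion falls in its gap. Only 9 lost clashes.
- **That 13 of 20 on measure acceptability is a realistic gap result.** The source-data table in section 16 takes acceptability from the semi-structured interviews, and section 12.2 limits these to 10 parents/carers and 10 therapists. Exactly 65% cannot arise from 10 or fewer parents/carers. Exactly 55% on intervention acceptability needs 11 of a full 20 respondents. The single-point gaps are minor drafting slips.
- **That these bands are the study's only decision output.** Section 5.2 also lists a manualised intervention, a description of usual treatment and choices of outcome measures.

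**Conclusion.** The point holds. As written, section 14.7 has one overlap (attrition above 40% and below 50%), four ten-point gaps (fidelity, outcome completion, item completeness, receipt of the intervention) and three single-value gaps. Its combination rule is ambiguous and it states no precedence. The overlap and gaps follow directly from the stated limits and need no assumption; the counts assume that all 20 participants are recruited.

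The direct attrition clash is uncommon, at about 6.5% if true attrition is 30%. The receipt gap could be more frequent, at about 7% to 34% for assumed true receipt of 85% down to 75%. The consequence is that the label put before the SSC would be settled after the data are seen. It is not that a go/no-go decision would be wrongly triggered.

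A reader might infer that the attrition boundary should be 50%, as the complement of the Red completion limit. The protocol does not support 50% over 40%, and section 5.2 describes retention by withdrawal, loss to follow-up and completion together, so attrition is not simply the complement of completion.

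**What to change.** Replace the prose of section 14.7 with one table of contiguous, non-overlapping bands.

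1. **Gaps.** Keep the stated Green and Red limits and define Amber as everything between them, with the ends assigned. This gives 50% to below 75% for fidelity, outcome completion and item completeness; 60% to below 90% for receipt; 55% to below 70% for intervention and consent acceptability; and 65% to below 75% for measure acceptability.
2. **Attrition.** The sponsor and the SSC should reconcile the 40% and 50% limits and record a single Amber/Red boundary with the reason for it.
3. **Accrual unit.** Reconcile the per-site limits with the overall plan in section 9.3, including the later-months alternative, and assign the value at the Red limit. This must come before step 4; otherwise a study recruiting exactly to plan would be Red.
4. **Combination and precedence.** State once: Green only if every sub-criterion is Green; Red if any is Red; otherwise Amber. The SSC's discretion over what follows can stay as it is.

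The cost is a wording amendment, with no change to data collection or sample size. It should be made and dated before Phase 2 results are reviewed. The protocol does not show whether that point has passed: section 9.6 expected Phase 2 to start around June 2021, and the current version was issued on 28 July 2021. If results have already been seen, the amendment should say so.

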We will also collect information about medication at baseline and post-intervention to test the feasibility of capturing this information. This information will be collected from carers and corroborated with prescribing clinicians as required. Any changes will be recorded and noted. We will also record and report data on accrual rates, attrition, response rates in relation to our measures. At this stage, we are not considering incorporating measures of quality of life or resource use as this would be incorporated into a future trial.

For our outcome instruments, we will examine the percentage of participants and carers who complete them at each time point, the percentage of items within each outcome measure for each participant that are completed, and the percentage who judge our outcome measures to be acceptable.

The outcomes from Phase 1a will be: (a) an adapted intervention manual that can be tested within a feasibility study (Phase 2), (b) a fidelity checklist, and (c) candidate outcome measures for use within the Phase 2 feasibility study.

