# Phase 2 (Feasibility Study)

Co-applicant [name] has developed an exposure-based intervention for children with severe LD and limited communication skills, and through a series of cases studies, has demonstrated successful treatment delivery and outcomes. This intervention, which is already designed to accommodate the necessary augmented communication strategies, as well as dealing with behavioural, repetitive, and sensory difficulties often experienced by this population, will form the basis of the intervention adapted in Phase 1.

Using the intervention developed within Phase 1 of the current study, we will complete a feasibility study to model the intervention and determine its acceptability and feasibility for stakeholders, including service users, parents/carers, and clinicians, as per the Medical Research Council (MRC) Framework for the development of complex interventions (53).

Design: A single arm, non-randomised, feasibility study, with participants who will receive the adapted intervention developed in Phase 1a. We propose to recruit 20 participants and their parental caregivers (N=20), who will receive the intervention, in conjunction with any other treatment they are currently receiving. Children currently receiving treatment for specific phobia or psychological intervention for other anxiety disorders will not be eligible to participate.

Participants will be assessed at three times points: (1) screening, (2) baseline assessment within 4weeks before commencement of the intervention, and (3) assessment at completion of the intervention. Additional components of feasibility (e.g. acceptability) will be assessed using semistructured interviews and qualitative analysis, described below.

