Setting, Context, and Trial Pathway: This single arm non-randomised feasibility study will take place within the NHS - either specialist LD or mainstream child and adolescent mental health services in England. We will use a multi-point recruitment strategy, including NHS services, special schools, and parent support groups, together with NIHR Clinical Research Networks. In addition, we will work with the Research in Developmental Neuropsychiatry (RADiANT) consortium of NHS providers to maximise recruitment. RADiANT is a consortium of NHS service providers which works in collaboration with academics in a number of universities. It seeks advice from service users, patients, families, charities, community leaders and a range of statutory bodies and organisations. RADiANT focuses on mental health and behavioural issues associated with five developmental conditions, including Learning Disability (LD) and Autism Spectrum Disorders (ASD). The consortium is co-convened by [name], Associate Dean, Royal College of Psychiatrists and [name], University of Warwick (and co-applicant on this proposal). The Coventry and Warwickshire Partnership NHS Trust and the Herefordshire Worcestershire Health and Care NHS Trust Learning Disabilities service have agreed to be a recruitment site. Using these existing networks will facilitate the timely recruitment of participants into the study.

The steps in the pathway for the feasibility study are as follows:

- a) all participants who consent to participate in the study will be screened by research staff to ensure they meet the inclusion criteria for the study (parent/guardian consent, child assent),
- b) following baseline assessment, participants who meet eligibility criteria will receive the intervention (plus treatment as usual),
- c) participants will be assessed using the study outcome measures within 4 weeks of completion of the intervention,
- d) a subsample of participants (parents/carers) and the therapists will be invited to take part in semi-structured interviews following completion of the intervention to further assess acceptability, their experience of the intervention, the study pathway, procedures, consent, and associated factors in order to provide a description of the factors that facilitate or challenge the implementation of the intervention,

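### Amber and Red completion rules in section 14.7 reuse Green's time-point wording, so on a per-time-point reading poor follow-up alone cannot trigger them once baseline is adequate

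*Protocol*

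**What the plan says.** Protocol section 14.7 sets three completion rules under (c)(i):

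- Green: "at least 75% of participants complete outcome measures at each time point"
- Amber: "less than 75% but greater than 60% of parents/carers complete outcome measures at each time point"
- Red: "less than 50% of parents/carers complete outcome measures at each time point"

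Green requires all its criteria. Amber applies if any of its criteria is met. Red opens with "If any of the following criteria are met, and following a thorough review of the reasons for this", after which the Study Steering Committee may recommend against a larger trial.

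Section 5.2 describes the statistic itself: "we will examine the percentage of participants and carers who complete them at each time point". In section 6, Phase 2, the assessments after screening are "baseline assessment within 4weeks before commencement of the intervention, and (3) assessment at completion of the intervention". The schedule in section 12.1 places the outcome measures at baseline and follow-up only. The pathway puts baseline before treatment: "following baseline assessment, participants who meet eligibility criteria will receive the intervention (plus treatment as usual". On size, section 14.3 says "We will recruit up to 20 participants and their parental caregivers in total".

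**The concern.** A requirement that every time point passes is broken as soon as one time point fails. Amber and Red should therefore respond to a failure at either time point. By repeating Green's phrase, they appear to ask for failure at both.

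Baseline is taken from families who have just agreed to join and have not yet started treatment, so it is the time point less likely to fail. Follow-up is where a larger trial would be exposed. If a good baseline switches off the Amber and Red completion rules, a shortfall confined to follow-up can leave the study outside Green without placing it in any band. These rules decide when the team must examine causes and remedies, and they inform the recommendation on a larger trial, so each should have one meaning.

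**Working it through.** There is no stated figure to reproduce; section 14.3 says no formal power calculation is made. The check applies the (c)(i) rules literally.

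**Inputs**
- N = 20 families, the maximum in section 14.3. Green counts participants while Amber and Red count parents/carers; with one caregiver per child these are the same 20.
- b = number completing baseline, f = number completing follow-up, with f no larger than b. Rates are b/20 and f/20.
- Bands from section 14.7: Green at least 75%, Amber above 60% and below 75%, Red below 50%.
- Attrition is taken as loss to follow-up under section 10.2 (follow-up data collection not completed): (20 − f)/20. Attrition limits in section 14.7: Green 30% or lower, Amber above 30% and below 50%, Red above 40%.

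**Reading 1: one rate per time point, both in the band** (the form in section 5.2)
- Red needs b/20 < 50%, so b ≤ 9, as well as f ≤ 9. Once b ≥ 10 (50%), no value of f meets Red (c)(i).
- Amber needs 60% < b/20 < 75%, so b = 13 or 14. Once b ≥ 15 (75%), no value of f meets Amber (c)(i).
- With b = 20, every f from 0 to 14 fails Green and meets neither Amber nor Red.

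**Reading 2: share of parents who complete at every time point**
- With b = 20 this share is f/20.

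**Results with b = 20**

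| f | Rate | Reading 1 | Reading 2 |
|---|---|---|---|
| 0–9 | 0–45% | no band | Red |
| 10–12 | 50–60% | no band | no band |
| 13–14 | 65–70% | no band | Amber |
| 15–20 | 75–100% | Green | Green |

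The 10–12 row is empty on both readings because the Red cut-off is 50% and the Amber floor is 60%. That is a separate gap.

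**The case that isolates the wording: b = 20, f = 14, all else Green**
- Attrition = 6/20 = 30%, which passes Green.
- Follow-up completion = 14/20 = 70%, below 75%, so Green (c)(i) fails.
- Amber (c)(i): follow-up at 70% is in the band, but baseline at 100% is not. Not met on reading 1.
- Red (c)(i): not met.
- Reading 2 gives Amber.

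Neither attrition nor the 50–60% gap explains this result; only the time-point wording does. The protocol does not say how item completion in (c)(ii) treats a follow-up set that was never returned, so its being Green here is an assumption.

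**How far attrition covers lower counts**
- f = 13: 7/20 = 35%, within the Amber attrition range.
- f = 8: 12/20 = 60%, above the Red limit of 40%.
- f = 0: 20/20 = 100%, above the Red limit.

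In both Amber and Red, however, the attrition item is joined to the accrual item by *and*, so it is unclear whether attrition alone triggers the band.

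**The case against.** A reader might infer that Red on completion can never be reached, even if nobody completes follow-up. The documents do not support that, for three reasons.

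- The Red sentence can be read in ordinary English as the share of parents who complete at every time point. On that reading 0/20 or 8/20 at follow-up is Red. Section 5.2 favours a rate per time point but does not say that Red needs failure at all of them.
- Even on the per-time-point reading, the block depends on baseline reaching 50% for Red or 75% for Amber. The protocol gives no baseline rate, and section 9.4 allows postal baseline collection.
- Red (c)(i) can still be met if 9 or fewer families complete baseline.

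A reader might also infer that poor follow-up would go unnoticed. That too goes beyond the text. Green (c)(i) fails, and Green needs every criterion. Section 10.2 counts a family that does not complete follow-up data collection as lost to follow-up, so attrition overlaps heavily with non-completion. Criterion (c)(ii) also reads completion, by items. Section 5.2 has completion examined at each time point, so the follow-up rate should be available to the committee, whose Red recommendation is discretionary.

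These points limit the harm but do not settle the wording. The same data, 20/20 then 14/20, give Amber on one reading and no band on the other, and the protocol does not choose.

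**Conclusion.** The fault holds, at moderate weight; it is not a must-fix. Read per time point, Amber and Red (c)(i) are not the complement of Green, and with N = 20 they cannot respond to follow-up alone once baseline completion is at least 15/20 (Amber) or 10/20 (Red). The clearest consequence is the 14/20 case: 70% completion lies inside the intended Amber range, attrition passes Green, and no (c)(i) band applies.

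This rests on the per-time-point reading, which section 5.2 supports but does not impose. It also rests on the assumption that baseline completion reaches those levels, which is plausible because baseline precedes treatment. For lower follow-up counts, attrition and item completion give partial cover; how much depends on how the *any* and *and* wording is meant.

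**What to change.** In section 14.7:

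- Leave the time-point condition in Green as it is.
- In Amber and Red (c)(i), apply the band to the time point with the lowest completion, baseline or follow-up.

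With baseline 20/20, follow-up of 0–9 is then Red, 13–14 Amber and 15–20 Green. Counts of 10–12 (50–60%) still fall between the Red and Amber cut-offs, so that gap must be closed in the same edit by assigning the range to one band.

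The cost is two phrases plus one cut-off. No data collection or procedure changes. The edit should be made before the completion data are judged against the criteria.
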